3.6. Adjustments for Covariates

Due to small sample size, no formal statistical analyses that adjust for possible covariate effects are planned. Exploratory subgroup analyses will be performed for descriptive purposes, as described in [Section 3.9](#).

3.7. Assessment of Clinical Benefit

As is noted in the literature, BPDCN is a rare hematologic malignancy that may represent less than 1% of cases presenting as AML, and has a multifaceted presentation involving manifestation in the BM and skin, and may also involve other organs including lymph nodes and other viscera. There are limited prospective data in this rare disease, with no standard of care treatment established. It is therefore important to assess the clinical benefit of potential new therapies through the analysis and interpretation of multiple clinically relevant endpoints.

Conventional chemotherapy alone historically has not resulted in long-term remissions in the majority of patients with BPDCN ([Pemmaraju 2015](#); [Pemmaraju 2014](#); [Pemmaraju 2012](#)); however, as noted in the literature, induction remission followed by bridge to stem cell transplant (SCT) has been shown to provide long-term remissions in certain patients and has been cited as a major, if not the key, therapeutic objective.

Allogeneic hematopoietic stem cell transplantation (allo-SCT) in BPDCN has been reported to be potentially beneficial in select BPDCN patients. Allo-SCT is ideally performed during first remission ([Aoki, et al. 2015](#); [Kharfan-Dabaja, et al. 2013](#); [Riaz, et al. 2014](#); [Roos-Weil, et al. 2013](#); [Shapiro 2015](#)). A large study using data from 86 first-line BPDCN patients recruited in the French network of BPDCN demonstrated a median OS for 34 patients who received SCT (40%) following CR (autologous SCT, 4 patients; or allo-SCT, 30 patients) of 49 months, against OS of 8 months for the 52 patients without SCT ($p < 0.0001$). The beneficial effect of SCT appeared to persist independently of age in multivariate analysis ([Poret 2015](#)). The Leukemia and Lymphoma Society in October 2016 stated that allo-SCT may result

in remissions that are longer, especially if offered after the first remission, and recommended that BPDCN patients be evaluated for SCT as soon as feasible. Dalle and colleagues ([Dalle, et al. 2010](#)) found that BPDCN patients who had SCT had a median OS of more than 40 months versus approximately 12 months for patients who did not receive SCT, and concluded that BM transplantation should be considered as a first-line treatment option when feasible. Similar results were seen in an analysis of 39 BPDCN patients from the European Blood and Marrow Transplantation Group (EBMTG) registry who underwent SCT as reported by Roos-Weil and colleagues ([Roos-Weil, et al. 2013](#)).

It is not clear from the literature how many patients with BPDCN are eligible for SCT, but it is generally known that candidates for allo-SCT are typically young, have a limited number of comorbidities, and have a suitable donor. Although limited data are available, promising results also have been seen with autologous SCT (auto-SCT), with 4 year OS and PFS rates of 82% and 73%, respectively, in a small (n=11) number of patients who underwent auto-SCT in first remission ([Aoki, et al. 2015](#)).

Ideally, to optimize the chances of SCT success, a patient ideally needs to be in remission following induction therapy and be considered to be ‘fit’ for the procedure based on the SCT guidelines. Accordingly, given that BPDCN is largely a disease of the middle aged and elderly, therapies that have an acceptable safety profile, are quickly effective, and allow for postremission transplantation of older patients with BPDCN are urgently needed and would be clinically beneficial ([Pemmaraju 2016](#)).

Control of BPDCN through reduction of blast cells in the BM may allow a patient to be bridged to SCT and thus is clinically meaningful, whether manifested as a component of a global CR, ie, CR among all compartments of disease present at baseline for patients with marrow disease ($\geq 5\%$ blast cells) at baseline, or as a CR in the BM compartment (BMCR) with PR in other non-BM compartment(s). As noted in the study protocol, a patient with BMCR is defined as having a complete BM response (reduction to $< 5\%$ blast cells), for patients with marrow disease ($\geq 5\%$ blast cells) at baseline, with either CR or PR in other non-BM compartments. Marrow disease, as in other aggressive hematologic malignancies, is a leading cause of morbidity and death in BPDCN and is also the major barrier to resumption of a meaningful quality of life (eg, due to the requirement for growth factor support, antibiotics, hospitalizations, etc). Further, resolution of disease in the BM, or maintenance of a lack of BM disease from baseline, may provide the opportunity for a bridge to SCT (ie, marrow must ideally be grossly disease-free for a patient to be considered for SCT), even if there is detectable disease in other compartments of BPDCN. Given that bridge to SCT is a major, if not the key, therapeutic objective of BPDCN therapy with evidence of long-term benefit in certain patients, we believe that clinically meaningful outcomes of induction therapy in BPDCN include either global CR or BMCR (with PR in other compartments) that lead to bridge to SCT ([Leclerc, et al. 2017](#)).

The proportion of patients who achieve a response of BMCR and the proportion of patients who receive SCT, should therefore, in our view, be considered as part of the overall key endpoints that provide evidence of clinical benefit of tagraxofusp in patients with first-line BPDCN. ([Leclerc, et al. 2017](#)).

In order to more completely demonstrate the clinical benefit of tagraxofusp, additional endpoints will be analyzed in a descriptive, supportive manner, including endpoints related to longer-term benefit such as PFS and OS, the proportion of patients who receive SCT and the extended duration of effect subsequent to SCT. These additional endpoint analyses will be

performed on the pivotal cohort of first-line BPDCN patients from Stage 3, as well as the larger pool of data from first-line BPDCN patients across all stages of the trial.

3.8. Efficacy Endpoint Analysis

3.8.1. Primary Endpoint

The primary evidence of efficacy is an analysis of the rate of CR, accompanied by an evaluation of the durability of response, including durability of these CRs, as a key secondary endpoint.

3.8.2. Secondary Endpoints

Formal hypothesis testing of secondary endpoints is not planned. The analyses of all secondary endpoints will be descriptive. The description of analyses to be performed by stage and pooling of stages is described in Section 3.5. Summaries of secondary endpoints to be evaluated and presented as follows:

1. BMCR and duration of BMCR
2. ORR (CR + CRc + CRi + partial response [PR]) and duration of objective response
3. Proportion of patients who receive an SCT
4. PFS
5. OS

Further detail on the definitions and analysis methods of primary and secondary efficacy endpoints is provided in [Section 4.3](#).

3.8.3. Exploratory Endpoints

Exploratory endpoints will be assessed to further evaluate efficacy, dependent on the extent of data available. These endpoints will include several additional time to event endpoints, including TTCR, TTR, time to BMCR, TTP, and RFS. Additional exploratory analysis may compare baseline disease severity between Stages and assess the respective impacts of baseline disease severity and compartments of disease expression over time on outcome measures such as CR rate and ORR. In addition, an exploratory efficacy analysis will be performed to assess the rate and duration of CR as defined per the Study Protocol Amendment 9 (09 February 2017), including CR + CRc + CRi.

Further detail on the definitions and analysis methods of exploratory efficacy endpoints is provided in [Section 4.3](#).

3.9. Subgroup Analyses

Efficacy analyses for Stage 4 and pooled Stages 3 and 4 as appropriate, will be summarized separately for those bridged to SCT and not bridged to SCT post-treatment. Efficacy analyses will also be summarized by baseline disease site (Skin only, Systemic only [Bone Marrow, Peripheral Blood, Lymph Node, or Visceral Disease], and Skin and Systemic).

Subgroup analyses will be performed for safety parameters in the FL and RR BPDCN populations, as specified in the below table. Subgroup analyses will be presented only when the minimum-sized subgroup classification includes at least 10% of the population.

Table 3-2: Subgroups and Definitions for Safety Analyses

Parameter	Description
Age	<65 vs. ≥65, <75 vs. ≥75 years of age
Sex	Male, Female
BMI	Obese: >30 kg/m ² Overweight: 25-30 kg/m ² Normal/Underweight: < 25 kg/m ²
Eastern Cooperative Oncology Group (ECOG) Performance Status	Baseline score of 0 Baseline score of 1 or 2

Subgroup analyses will be performed for the following safety summaries:

Overview of adverse events (AE)
Treatment emergent AEs by system organ class (SOC) and preferred term (PT) (occurring in at least 15% of population)

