3.7.2 Current Study (STML-401-0114)

Stage 1 of STML-401-0114 employed a traditional 3+3 design and has been completed. A total of 23 patients were enrolled in Stage 1, of whom 9 had BPDCN and 14 had R/R AML. SL-401 was investigated at doses of 7, 9, 12, and 16 µg/kg/day IV for up to 5 consecutive days every 21 days (i.e., a multi-cycle regimen). (Only patients with AML received SL-401 at doses of 9 and 16 µg/kg/day.) The maximum tested dose of SL-401 in patients with BPDCN was 12 µg/kg/day; an MTD was not identified in BPDCN.

A complete summary of all AEs attributed to SL-401, including DLTs seen in Stage 1 of the study, is available in the most recent version of the SL-401 Investigator Brochure.

An analysis of safety data available through 28 July, 2016, for 26 patients with BPDCN showed that, overall, 24 (92%) patients have experienced at least 1 treatment-emergent adverse event (TEAE), with 22 (85%) patients experiencing at least 1 ≥Grade 3 TEAE. The most common TEAE was transaminase elevation (either ALT increased [62%] or AST increased [58%]). Overall, 17 (65%) patients have experienced ALT increased and/or AST increased, with these events also being the most common ≥Grade 3 TEAE (each 54%), treatment-related TEAE (54%), and treatment-related ≥Grade 3 TEAE (50%). Transaminase elevations were largely transient and not dose-limiting.

Other most commonly reported TEAEs, regardless of relationship to study drug, were nausea and peripheral edema (each 46%); fatigue, hypoalbuminemia, and pyrexia (each 42%); chills (35%); and anemia and hyperglycemia (each 31%).

The frequency and type of TEAEs were similar between the 12 µg/kg/day and 7 µg/kg/day dose groups, with no indication of dose-relationship.

Twelve (46%) of 26 patients experienced at least 1 serious adverse event (SAE). The only SAEs reported for >1 patient were CLS, pyrexia, and respiratory failure (each 2 patients).

Please consult the most recent SL-401 Investigator Brochure for comprehensive and up-to-date information concerning the safety profile associated with SL-401.

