4.4. Safety Analyses

With the exception of Subgroup Analyses ([Section 3.9](#)), all safety tabulations will be presented by disease (first-line BPDCN, R/R BPDCN, AML) for all patients in the Safety Population by stage of enrollment (all doses included). All safety tabulations will be presented for first-line BPDCN patients in the Safety Population who were treated at 12 µg/kg/day by stage of enrollment and for those treated with lyophilized formulation of tagraxofusp.

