4.4.2.1. Capillary Leak Syndrome

In addition to the summaries described in [Section 4.4.2](#), summaries will be provided that include:

- Summary of number of CLS events, exposure to tagraxofusp prior to onset of CLS, and time to first onset and time to resolution of CLS events;
- Summarized incidence of albumin infusions and timing of infusions in relation to CLS onset;
- Plots of liver function and albumin laboratory values over time for patients who experience CLS;
- Comparison of demographic characteristics of patients who experience AESI of CLS to those who do not

Additionally, analyses of capillary leak syndrome will be provided based on an FDA algorithm, found in [Section 8.3](#).

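### The 15% display rule for adverse-event terms in the safety subgroup tables is set on the whole line-of-therapy population, so it can hide an event concentrated in a small subgroup

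*SAP*

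**What the plan says.** SAP 3.9 sets the scope of the safety subgroup work: "Subgroup analyses will be performed for safety parameters in the FL and RR BPDCN populations, as specified in the below table". Table 3-2 lists four factors: age ("<65 vs. ≥65, <75 vs. ≥75 years of age"), sex, BMI in three classes, and baseline ECOG 0 against 1 or 2. A size rule follows: "Subgroup analyses will be presented only when the minimum-sized subgroup classification includes at least 10% of the population".

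Two outputs are then named. One is "Overview of adverse events (AE"), with no frequency limit. The other is "Treatment emergent AEs by system organ class (SOC) and preferred term (PT) (occurring in at least 15% of population"). No exemption is given for serious events, Grade 3 or higher events, or adverse events of special interest (AESIs).

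Outside 3.9, the layout is different. SAP 4.4 says that, subgroup analyses apart, "all safety tabulations will be presented by disease (first-line BPDCN, R/R BPDCN, AML) for all patients in the Safety Population by stage of enrollment". The serious, Grade 3 or higher and AESI summaries in 4.4.2 carry no 15% limit, but they are organised by disease, line and dose. SAP 4.4.2.1 adds one term-specific look at patient characteristics: "Comparison of demographic characteristics of patients who experience AESI of CLS to those who do not".

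**The concern.** The purpose of a subgroup table is to show terms whose rate differs between classes. A filter on the pooled rate works against that, because the pooled rate averages the small class with everyone else. The two percentages in 3.9 also pull against each other: a class may be admitted at 10% of the population, yet a term needs 15% of that population to earn a row.

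At stake is how a missing row is read. Someone looking for a specific toxicity in patients aged 75 or over, or with ECOG 1 or 2, may take its absence as no difference between classes, when the display rule removed the term. SAP 4.4.2 uses 10% to define common events in the main tables, so the table meant to find differences has the stricter limit.

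**Working it through.** The documents give no sample size or operating figure for these tables, so there is no stated figure to reproduce.

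**Reading of population.** In 3.9 the word denotes the first-line or relapsed/refractory BPDCN group, and subgroup classes are parts of it. The 15% limit is read the same way.

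**Inputs.**
- First-line: 19 in Stages 1 and 2 (SAP 3.13.1), 13 enrolled in Stage 3 and 37 treated in Stage 4 (SAP 3.1). Sum: 69, all doses.
- Relapsed/refractory: 13 + 5 = 18 (same sections).
- Number aged 75 or over: not given. Assumed 14 of 69 (20%), with 10 and 21 (about 15% and 30%) as the range.
- Rate in the remaining patients: assumed 5%.

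**Step 1, count needed.** First-line: 0.15 × 69 = 10.35, so 11 patients. Relapsed/refractory: 0.15 × 18 = 2.7, so 3 patients.

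**Step 2, what can be hidden with no event elsewhere.** No event rates need to be assumed.

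| Group | Class size | Largest hidden count in class | Rest | Pooled rate |
|---|---|---|---|---|
| First-line | 7 (10%) | 7/7 (100%) | 0/62 | 10.1% |
| First-line | 14 (20%) | 10/14 (71%) | 0/55 | 14.5% |
| First-line | 21 (30%) | 10/21 (48%) | 0/48 | 14.5% |
| First-line | 28 (40%) | 10/28 (36%) | 0/41 | 14.5% |
| Relapsed/refractory | 2 (11%) | 2/2 (100%) | 0/16 | 11.1% |

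A first-line class of 7 to 10 patients passes the 10% rule, but even if every member has the event the count stays below 11.

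**Step 3, chance that a real difference is dropped.** For a class of size n with true rate p, 5% in the other 69 − n, and independent patients:

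P(dropped) = Σₐ P[Bin(n, p) = a] × P[Bin(69 − n, 0.05) ≤ 10 − a].

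| Class size | 30% vs 5% | 40% vs 5% | 50% vs 5% |
|---|---|---|---|
| 10 | 97% | 94% | 87% |
| 14 | 93% | 81% | 63% |
| 21 | 76% | 47% | 19% |
| 35 (about half) | 29% | 5% | 0.3% |

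**Step 4, sensitivity to the denominator.** Protocol 3.7.2 gives 16 first-line patients at 12 µg/kg/day in the interim analysis. Then N = 16 + 13 + 37 = 66 and the count needed is 10 (0.15 × 66 = 9.9). With 14 in the class, the drop probabilities are 88%, 71% and 49%.

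**The case against.** The strongest reply is that this is a display threshold in an exploratory table. SAP 3.6 calls the subgroup work descriptive because numbers are small, and a table limited to terms reaching 15% does not claim to rule out rarer toxicities. The adverse-event overview is run by subgroup without a limit. The full serious, Grade 3 or higher and AESI tables and the by-patient listings still contain every event. SAP 4.5 also plans event counts by antibody status and titre rise. All of that is true. None of it gives a comparison of named terms by age, sex, BMI or ECOG, except capillary leak syndrome by demographics.

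The size also depends heavily on the class. Protocol 3.1 gives a median age at diagnosis of 66, so the split at 65 may divide the group roughly in half, where the loss is modest (last row of Step 3). This stands: the problem is one of small classes.

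A reader might go further in three ways that the documents do not support.
- That concentrated events are always removed. They are not: 60% in a class that is 30% of the population is 18% pooled and is shown.
- That the protocol's own serious events would fall below the limit. Protocol 3.7.2 says "The only SAEs reported for >1 patient were CLS, pyrexia, and respiratory failure (each 2 patients"), which is 2 of 26 each. But the limit applies to treatment-emergent events of any seriousness. Pyrexia occurred as such in 42%, capillary leak syndrome has its own analysis, and the overall rate of respiratory failure is not given.
- That only mild terms survive. ALT and AST increases were among the most common terms and reached Grade 3 or higher in 54% each.

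**Conclusion.** The concern holds in a conditional form. The rule in SAP 3.9 can hide a term-level difference when the affected class is small, and it must do so when the event is confined to a class of 10% to just under 15% of the population. That last statement follows from the two percentages alone. The probabilities for patients aged 75 or over rest on an assumed class size, an assumed 5% background rate, independent patients, and a denominator of about 69. That denominator is a sum of documented counts, with the Stage 3 count being patients enrolled, not confirmed as treated.

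The reading of population as the undivided line-of-therapy group follows the usage in 3.9 but is not stated there; if something else was meant, the wording needs correcting anyway. The events are not lost from the report. What is lost is their comparison across these factors. No primary or secondary efficacy result is affected. The change is worth making because it is cheap and the present rule works against the table's purpose.

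**What to change.** In SAP 3.9, replace the 15% condition with the following:
- Show a term in a factor's table if it reaches 15% in any class of that factor, with at least 2 patients affected in that class.
- Always show AESI terms, and any term with a serious or Grade 3 or higher event in two or more patients, whatever the overall rate.
- State that the tables are descriptive, and that an absent row does not show equal rates.

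**Effect.** In a class of 14 the limit becomes 3 patients (0.15 × 14 = 2.1), and in the other 55 it becomes 9 (0.15 × 55 = 8.25). A 30% vs 5% term then appears with probability 84%, against 7% (100% − 93%) under the present rule. A 50% vs 5% term appears with 99%, against 37%.

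**Cost.** SAP wording and longer tables; no new data. More rows will rest on small counts. In a class of 10, a term with a uniform 5% rate reaches 2 patients by chance 8.6% of the time. The 2-patient minimum matters most for relapsed/refractory patients: in a class of 6 or fewer, one event is already at least 16.7% (1/6), and without the minimum every single occurrence would fill a row.

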3.10. Withdrawals, Dropouts, Loss to Follow-up

Patients who are withdrawn or discontinue from the study will not be replaced.

3.11. Missing, Unused, and Spurious Data

In general, there will be no substitutions made to accommodate missing data points. All data recorded on the eCRF will be included in data listings that will accompany the CSR.

When tabulating AE data, partial dates will be handled as follows. If the day of the month is missing, the onset day will be set to the first day of the month unless it is the same month and year as study treatment. In this case, in order to conservatively report the event as treatment-emergent, the onset date will be assumed to be the first day of treatment. If the onset day and month are both missing, the day and month will be assumed to be January 1, unless the event occurred in the same year as the study treatment. In this case, the event onset will be set to the first day of treatment in order to conservatively report the event as treatment-emergent. A missing onset date will be set to the first day of treatment.

3.12. Visit Windows

It is expected that all visits should occur according to the protocol schedule. All data will be tabulated per the evaluation visit as recorded on the eCRF even if the assessment is outside of the visit window. In data listings, the relative day of all dates will be presented (see [Section 3.2](#)).

3.13. Timing of Analyses

3.13.1. Interim Analyses

A preliminary and informal interim analysis was performed on efficacy data from Stages 1 and

2

This analysis was performed on the 32 BPDCN patients (19 first-line and 13 R/R) enrolled

in the study prior to 29 August, 2016, 3 of whom were treated with tagraxofusp 7 µg/kg/day and 29 were treated with tagraxofusp 12 µg/kg/day. The ORR, CR rate, PFS, and OS efficacy parameters were summarized. Selected safety summaries also were presented.

Note that no further enrollment of first-line BPDCN patients occurred until October 26, 2016.

[REDACTED] first-line BPDCN patients enrolled on or after October 26, 2016 (with enrollment period later defined as between October 26, 2016 and March 17, 2017) will be considered as a separate, pivotal patient cohort for statistical analysis, as previously described in [Section 1.2.1](#).

In Stages 2-4 of the study, the Data Safety Review Committee (DSRC) was to conduct a safety data review every 1-2-months.

3.13.2. Independent Review Committee

An Independent Review Committee (IRC) has been established to review tumor responses and duration of response for patients with BPDCN enrolled in Protocol STML-401-0114.

Response is best assessed by the treating investigator because disease-compartment responses, and in particular bone marrow responses, are used in the real-time management of the patient. It is also important to verify to the extent possible that the protocol-specified response criteria have been applied objectively and uniformly, therefore the IRC will apply the protocol specified response criteria to provide consistent and independent evaluation of tumor responses by cycle and overall. The IRC evaluation, which will be considered as supportive to the primary assessment of response by the investigator, was performed on 28-29 August 2017, prior to the primary efficacy, safety, PK, and immunogenicity analysis. The IRC is governed by a separate charter.

